### *Exclusion criteria for all Participants:*

- History of head trauma with LOC > 30 minutes, or with a penetrating head wound, or with moderate to severe memory or other cognitive impairment.
- Neurological disorders: multiple sclerosis, epilepsy, stroke, PD, other degenerative CNS disorders, or neuropathy with radicular involvement.
- Acute or chronic major psychiatric disorders: schizophrenia, bipolar disorder or severe major depressive disorder, or severe anxiety disorder except PTSD and panic disorder (PTSD and depressive symptoms are common co-morbid conditions for combat mTBI and a subset of these patients have symptoms consistent with panic disorder as well).
- Use of illegal drugs; alcohol abuse within the past 6 months.
- Poorly controlled hypertension, heart failure, coronary heart disease, peripheral artery disease, carotid artery disease, diabetes mellitus, pulmonary disease with hypoxia or hypercapnia,

significant hepatic disease or hepatitis C seropositivity, renal failure, treatment for cancer, HIV positive, active infectious disease or presence of abdominal aortic aneurysm.

- Contraindications to LP (e.g., spinal cord injury; deformity, severe disease or infection in the region of the lumbosacral spine; bleeding tendency, use of anticoagulant medications, or platelet count <100,000/mm^2).
- Receiving medication in an investigational drug study.
- Exclusionary medications (used in the 4 weeks prior to screening):
  - Fibrates and niacin due to increased risk for myopathy in combination with statins;
  - Potential drug-drug interactions with statins via effects on CYP3A4: itraconazole, ketoconazole, erythromycin, clarithromycin, HIV protease inhibitors, nefazodone, amiodarone, cyclosporine, isoniazid, quinidine, or large quantities of grapefruit juice (>1 quart daily);
  - Selected CNS-acting medications: antipsychotics, anti-Parkinson's disease medications and CNS stimulants
  - Other medications affecting coagulation and/or inflammation: coumadin, potent anti-inflammatory medications (hydrocortisone, methotrexate or other potent immune-modulating medications), and anti-HIV medications.
- All female subjects of childbearing potential will undergo a urine pregnancy test at every subject visit; subjects with positive pregnancy test results will be excluded. In addition, all female subjects of childbearing potential will be required to use a reliable method of contraception throughout the duration of the study.

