To monitor for emergence or worsening of comorbid depression, the PHQ-9, a self-report measure of depression will be administered at all visits. The PHQ-9 score can range from 0 to 27. Scores of 5, 10, 15 and 20 represent thresholds demarcating the lower limits of mild, moderate, moderately severe and severe depression, respectively. If the PHQ-9 score is increased by 10 (i.e., an increase of two severity categories) compared to baseline, the subject will be terminated from the study. To monitor alcohol use and symptoms of comorbid PTSD, we will administer the AUDIT-C and the PCL-M at all visits.

If at any time during the study, a participant complains of symptoms which may indicate a potential adverse event, additional safety visit(s) as necessary will be performed. Procedures to be performed at additional visits will depend on the symptoms the participant is experiencing. If the participant meets any criterion for study removal (as described below), an early discontinuation visit will be performed.

**Early treatment discontinuation procedures:** The primary reasons for treatment discontinuation anticipated during the study are adverse effects, protocol violation, noncompliance, and withdrawal of consent. We will make every reasonable effort to keep each subject in the study. Every effort will be made to schedule a discontinuation visit as soon as possible following discontinuation of study medication to allow collection of outcome and safety measures.

**Criteria for termination from study:** Subjects will be removed from the study if they: 1) develop a significant adverse medication reaction, including psychiatric adverse effects; 2) exhibit >1 standard deviation decline on more than one component of the neuropsychological test battery; 3) develop a significant elevation in serum transaminases (i.e., > 3 X upper limit of normal for SGOT and/or SGPT) or CPK (i.e., > 10 X upper limit of normal); 4) have a positive urine pregnancy test; or 5) meet NCEP/ATP-III criteria for initiation of lipid-lowering therapy at the 3- or 6-month safety visits.

**Compliance with study medications:** Subjects will be given a 6-week supply of medication at Baseline and at the 6-week visit, and subjects will be given 3-month supplies of medication at the 3-, 6- and 9-month

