Subjects will come to the research clinic for regular monitoring. At each visit, a qualified licensed clinician will ask subjects if they have experienced any adverse events, specifically if they have experienced any unexplained muscle pain, or weakness. Any adverse event will be reported to the PI, or if the PI is not available, an alternative MD investigator. Subjects will be encouraged to call a study clinician at any time if they are experiencing any side effects. Subjects will also be provided with 24-hour emergency contact information.

LFTs, CPK, and HbA1c levels will be measured at 6 weeks and after 3-, 6-, 9-, and 12- months of treatment. The PI will review the laboratory results for every subject within 24 hours of the study visit. If the PI is not available, an alternative MD practitioner will review the laboratory results. If SGOT or SGPT values are  $\geq 3$  times the upper limit of normal, or if CPK levels are  $\geq 10$  times the upper limit of normal, study drug will be discontinued and subjects will be followed until laboratory values return to normal.

To monitor for potential cognitive side effects, we will perform the MoCA (a brief but sensitive global cognitive test) at all safety visits. If a subject reports problems with memory or cognitive function after initiation of study medication sufficient to interfere with daily function or MoCA score decline of one standard deviation or greater compared to Baseline, we will perform a thorough neurological and psychiatric examination and will

administer the entire neuropsychological battery. If a decline of one standard deviation or greater compared to Baseline is present on any test, the subject will be terminated from the study.

To monitor for emergence or worsening of comorbid depression, the PHQ-9 will be administered at all visits. The PHQ-9 score can range from 0 to 27. Scores of 5, 10, 15 and 20 represent thresholds demarcating the lower limits of mild, moderate, moderately severe and severe depression, respectively. If the PHQ-9 score is increased by 10 (i.e., an increase of two severity categories) compared to baseline or if the subject develops suicidal ideation with intent, the subject will be terminated from the study. To monitor alcohol use and symptoms of comorbid PTSD, we will administer the AUDIT-C and the PCL-M at all visits.

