#### **(5) Data Safety and Monitoring Plan**

(a) Monitoring of Subject Safety: Participant safety will be monitored as described above. Participants will be given 24 hour emergency contact information and will be instructed to call if they experience any AE during the study. In addition, subjects will be called by a study clinician within 24 hours after lumbar puncture to enquire about any adverse events, specifically lumbar puncture headache.

All AEs and serious AEs (SAEs) will be recorded at each visit and communicated to the study PI. Unanticipated AEs (physical complaints that are not present at baseline) and AEs which are more serious than anticipated, but are not SAEs will be reported to the IRB at the time of the annual report. SAEs (defined as any untoward medical occurrence at any dose that results in subject death, is life threatening, requires hospitalization, or results in persistent or significant disability/incapacity) will be reported to the IRB within 5 business days of being reported to the PI.

We recognize that a majority of these Veterans with mTBI will also have comorbid PTSD and/or depression; thus there is the possibility of worsening of their mental health status during study participation. Any participant who develops dangerousness toward self or others or emergence of acute symptoms necessitating hospitalization will be discontinued from study participation if these events occur during the period of data collection and then reevaluated for appropriateness for continuing in the study following reestablishment of psychiatric stability.

All participants will receive follow-up per their primary mental health care provider or will be referred for appropriate follow-up if they do not have a primary mental health care provider at study entry.

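### The PHQ-9 termination rule equates a 10-point rise with a two-category rise, but on the plan's own scale the two differ, and from a baseline of 18 neither can be met

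*Combined protocol and SAP*

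**What the plan says.** Under Study procedures, Monitoring safety of participants, the protocol gives the scale ("The PHQ-9 score can range from 0 to 27") and the bands ("Scores of 5, 10, 15 and 20 represent thresholds demarcating the lower limits of mild, moderate, moderately severe and severe depression, respectively"). The trigger follows, "If the PHQ-9 score is increased by 10 (i.e., an increase of two severity categories) compared to baseline", and its consequence is that "the subject will be terminated from the study".

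Section (2)(b), Protection Against Risk, repeats the trigger in the same words and adds a second one: "compared to baseline or if the subject develops suicidal ideation with intent, the subject will be terminated from the study".

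Entry is limited by diagnosis. The exclusion criteria list "schizophrenia, bipolar disorder or severe major depressive disorder, or severe anxiety disorder except PTSD and panic disorder", and screening uses the SCID-IV to identify excluded disorders. No PHQ-9 ceiling is stated, and Table 3 first schedules the PHQ-9 at the second baseline visit. The Data Safety and Monitoring Plan expects that "a majority of these Veterans with mTBI will also have comorbid PTSD and/or depression".

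Under Statistical analysis, the primary analysis is confined to randomized subjects who completed the study. Subjects who stop early enter only a secondary mixed-effects model.

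**The concern.** The parenthesis presents the category rise as a restatement of the point rise. If the two are not the same event, two staff members following the text in good faith can reach opposite decisions on the same pair of scores. The rule also compares a bounded score with its own baseline, so it must become unattainable at some entry score, and the plan does not say what happens there.

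Two things are at stake. First, this is a safety-removal threshold, and its stated purpose is to detect new or worsening depression. Second, removal decides whether a subject is a completer and therefore whether that subject is in the primary analysis set. A rule that can be applied in two ways makes membership of that set depend on interpretation.

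**Working it through.** **Inputs**, all from Monitoring safety of participants: score range 0 to 27; lower limits of bands 5, 10, 15 and 20. This gives five bands: 0-4, 5-9, 10-14, 15-19 and 20-27.

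**Definitions**, with baseline b and follow-up f:
- Points wording: f − b ≥ 10.
- Category wording: band(f) − band(b) ≥ 2.

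**The plan's equivalence, tested first.** Take a rise of exactly 10. For every b from 0 to 14 it moves the subject exactly two bands (0 to 10, 9 to 19, 14 to 24). For b = 15, 16 and 17 it moves the subject one band (15 to 25, 16 to 26, 17 to 27). So the parenthesis describes a 10-point rise correctly up to a baseline of 14 and not above. In the other direction, a rise of exactly two bands can be anything from 6 points (4 to 10, 9 to 15, 14 to 20) to 17 points (10 to 27). The equivalence is not reproduced.

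**Pairs meeting the points wording.** Each baseline b from 0 to 17 allows f from b + 10 to 27, which is 18 − b values. The sum is 18 + 17 + … + 1 = 18 × 19 / 2 = 171.

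**Pairs meeting the category wording.**
- b = 0-4 needs f of 10-27: 5 × 18 = 90
- b = 5-9 needs f of 15-27: 5 × 13 = 65
- b = 10-14 needs f of 20-27: 5 × 8 = 40
- b = 15 or more: none
- Total 90 + 65 + 40 = 195

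**Overlap.** For b = 0-14 every rise of 10 or more also meets the category wording. The points-only pairs are therefore those at b = 15, 16 and 17: 3 + 2 + 1 = 6. Pairs meeting both: 171 − 6 = 165. Category-only pairs: 195 − 165 = 30. Pairs meeting at least one: 165 + 30 + 6 = 201. Pairs meeting only one: 30 + 6 = 36.

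**Attainability by baseline.**

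| Baseline | Largest possible rise | Points wording | Category wording |
|---|---|---|---|
| 0-14 | 13 to 27 | can be met | can be met |
| 15-17 | 10 to 12 | can be met | cannot be met |
| 18-27 | 0 to 9 | cannot be met | cannot be met |

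**Can such baselines enter?** The exclusion is a diagnosis made by interview, not a score. Even if it were read as excluding the plan's severe band (20 and above), scores of 15-19 carry the label moderately severe and would remain eligible. That includes 18 and 19, where neither wording can be met.

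**The case against.** The strongest reply is that there is only one rule. The operative words are numeric, the parenthesis is a gloss, and the gloss is right for a 10-point rise wherever two higher bands exist. On that reading the 30 category-only pairs arise only if staff treat the gloss as a separate test. This is a plausible default reading, and it stands as such. But the text asserts equivalence, both sections repeat it, and the numbered list under Criteria for termination from study does not mention the PHQ-9 rule, so nothing in the documents says that the number prevails.

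A reader might infer that subjects with high entry scores have no psychiatric safeguard. The documents do not support that. Removal also follows from psychiatric adverse effects (Criteria for termination from study), suicidal ideation with intent (Protection Against Risk), a need for psychiatric intervention to manage deterioration (Safety procedures specific to the war zone population), and dangerousness or acute symptoms needing hospitalization (Data Safety and Monitoring Plan). Suicidal ideation is asked about at each visit. These subjects lose one score-based trigger, not psychiatric protection. A ceiling is also inherent in any fixed change rule on a bounded scale; the gap is that its handling is unstated.

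A reader might also take 36 of 201, or 18%, as a share of patients. It is not: it weights a move from 0 to 27 the same as a move from 9 to 15. The expectation of comorbid PTSD and/or depression does not show that scores of 18 or more will be common, and excluding severe major depressive disorder should reduce them.

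On the analysis, a discontinuation visit is planned to collect outcomes, and the secondary mixed model uses early-termination data. This softens the effect of an inconsistent removal rule but leaves the completer-based primary analysis exposed.

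**Conclusion.** The point holds, within limits. The rule is internally inconsistent on the plan's own range and cut-points. The two wordings disagree for some score pairs at baselines 0-14 (a two-category rise of 6 to 9 points) and for every 10-point rise at baselines 15-17; neither can be met from 18 upward. It would be wrong to say that neither wording can be met by all high scorers, because at 15-17 the points wording still can. It would also be wrong to say that the two sections conflict on the PHQ-9 trigger: that wording is the same in both, and they differ only in the added suicidal-ideation trigger.

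The arithmetic is exact and needs no assumption beyond integer scores and reading each wording as at least 10 points or at least two categories. The number of subjects affected cannot be estimated, because the documents give no PHQ-9 distribution at baseline or follow-up. The effect on the primary analysis is therefore one of direction only: the choice of wording changes who can be a completer, by an unknown amount. The matter should be corrected because it is a stated removal threshold and the correction is cheap.

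**What to change.** Reconcile the wording inside the rule to a single definition, in points or in categories, and use identical text under Monitoring safety of participants and Protection Against Risk. Delete the other definition or mark it plainly as illustrative. Have the investigators and the DSMB state how the rule applies to subjects whose baseline makes it unattainable: 18 or more if points are kept, 15 or more if categories are kept. Which definition and threshold to use is a clinical decision for them.

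The cost is a short amendment to two places. No new data are needed, since Table 3 already schedules the PHQ-9 at the second baseline visit and at every safety visit.

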### **Biomarkers:**

Overview: The primary outcome measures are biomarkers in CSF: t-tau, p-tau181, p-tau181:t-tau ratio, and BDNF. The secondary outcomes are additional CSF biomarkers of amyloid dysregulation: A $\beta$ 42; oxidative stress: F2-isoprostanes; and neuroinflammation: IL-6, IL-8, and S100 $\beta$ . All subjects will also undergo APOE genotyping. For each substance measured in CSF or blood, all study samples (i.e., from the baseline and from the 12 month follow-up visit) from any one subject and equal numbers of samples from subjects in the statin and placebo groups will be assayed within a single assay to reduce inter-assay variability. All samples will be measured blind to treatment assignment.

Blood collection for DNA and plasma and serum biomarkers: On the day of LP at baseline and at the 12 month follow-up visit, subjects will undergo blood collection for plasma and serum for biomarkers. Thirty five ml of blood will be collected into pre-chilled tubes containing EDTA and placed on ice. These samples will be cold centrifuged within one hour of collection, aliquoted into polypropylene tubes and frozen at -70 degrees C until assayed. Twenty ml of blood will be collected into plain glass tubes and sent to the VA Puget Sound clinical laboratory for the measurement of total cholesterol, HDL, LDL, homocysteine, and C-reactive protein (CRP).

At the screen visit only, 30 mls of blood will be collected into unchilled tubes containing EDTA and sent to [name] laboratory at VA Puget Sound for DNA preparation and APOE genotyping. Clinical lab analysis will take place at VA Puget Sound. All plasma and serum samples for biomarker analysis will also be accessioned, inventoried, and stored at -70 degrees C at VA Puget Sound S until assayed.

APOE genotyping will be performed by the UW ADRC Genetics Core under the direction of [name]. APOE genotyping will be performed using previously described PCR conditions and the HhaI restriction digest method.

Lumbar puncture for CSF collection: Following blood collection, CSF will be obtained using procedures developed and characterized in our laboratory as minimally invasive and well-tolerated by research participants (post-LP headache incidence <1%). Subjects will be placed in the lateral decubitus position. The L3-4 or L4-5 interspace will be infiltrated with 1% lidocaine to provide local anesthesia. A 24g Sprotte atraumatic spinal needle will be used to obtain 28 ml of CSF, which will be collected under negative pressure into sequential 6ml polypropylene syringes. The first three ml of CSF will be sent to the hospital laboratory for cell count and measurement of protein and glucose concentration. The remaining 25 ml of CSF will be divided into 0.5 ml aliquots into polypropylene tubes, frozen immediately on dry ice at the bedside, and then stored at -80 degrees C until assayed. Subjects will remain at bed rest for one hour after lumbar puncture and will be instructed to avoid any exertion for 48 hours.

Detailed methods for measuring CSF biomarkers: All CSF biomarkers will be measured in the laboratory of [name] at the University of Washington. Frozen samples will be taken from VA Puget Sound to [name] laboratory using approved leak-proof containers by personnel using universal precautions. Primary outcome measures will be change in concentration pre- to post-treatment of CSF tau, p-tau181, and BDNF. CSF A $\beta$ 42, F2-isoprostanes, IL-6, IL-8, and S100 $\beta$  will be secondary measures. For each CSF protein measured, pre- and post-treatment samples from any one subject and equal numbers of samples from subjects in each treatment group will be assayed within a single assay to reduce inter-assay variability. All samples will be measured blind to subject medication assignment.

Analyses of CSF BDNF, t-tau and p-tau181 proteins, concentrations of F2-isoprostanes, IL-6, IL-8, S100 $\beta$ , and A $\beta$ 42 on unthawed samples will be performed using immunobead-based multiplex assays. Panels of capture antibody-coated beads and labeled detection antibodies are purchased from two sources: Biosource Division of Invitrogen, Camarillo, CA, and Linco Research Inc., St. Charles, MO. The assay systems are run according to the instructions provided by each manufacturer and data is collected using a LiquiChip

Workstation from Qiagen (Valencia, CA). Standard curves for each protein are generated using the reference proteins supplied in these kits, and CSF concentrations interpolated from these standard curves.

CSF concentrations of F2-isoprostanes will be measured using a stable isotope dilution method with gas chromatography (GC) and mass spectrometry (MS) with selective ion monitoring (SIM) and [H4]15-F2t-isoprostane as an internal standard, as previously described. This oxidized and cyclized lipid product of arachidonic acid is an excellent quantitative *in vivo* biomarker of oxidative damage.

CSF will be banked at VA Puget Sound for future research, such as proteomic analysis before and after statin treatment. Proteomics, similar to genomics, is an unbiased method that simultaneously assesses thousands of proteins. Although there are several CSF biomarkers that reflect particular facets of neurodegeneration, it is unlikely that statins affect only a single or a small group of molecules. Thus, conducting a large scale survey of potential CSF biomarkers before and after statin treatment will allow us to define an ensemble of biomarkers that may discriminate treatment effects and provide insight into as yet unknown mechanisms of action. In addition, samples will be made available to other investigators nationally and internationally for research in neurodegenerative disorders. Samples will only be shared after appropriate Materials Transfer Agreements are executed. No identifying information will be included with any shared samples without subject consent.

**Neurocognitive and Behavioral Measures** (*Note: NINDS CDE and all other cognitive and behavioral measures are commonly used in similar studies; because of space limitations for references, the measures are described but not referenced*):

**Behavioral, functional and quality of life measures:** The SCID-IV will be administered at screening only to rule out exclusionary psychiatric conditions. Comorbid PTSD will be assessed using the CAPS at baseline and after 12 months of treatment and the PCL-M at all study visits. Current mTBI symptoms, functional status, and health-related quality of life will be quantified using the Brief Symptom Inventory (BSI), the Rivermead Postconcussive Questionnaire (RPQ), the Neurobehavioral Symptom Inventory (NSI), Satisfaction with Life Scale (SWLS) and the Craig Handicap and Assessment Reporting Technique (CHART-DF). The PHQ-9 and AUDIT-C will be administered at all study visits to assess depressive symptoms and alcohol use.

**Neurocognitive Battery:** We will use measures from the NINDS CDE as well as additional measures for assessment of neurocognitive function. The neurocognitive test battery includes measures of learning and memory, attention and information processing speed, and executive function. In addition, we will employ a measure of test effort (the Test of Memory Malingering [TOMM]) to provide an estimate of the validity of subject's test scores. If a subject's score on the TOMM suggests inadequate test effort, the rest of neurocognitive test scores will be considered invalid. The estimated time to complete the entire test battery is two hours. The complete neurocognitive battery will be administered at baseline and after 12 months of treatment with simvastatin or placebo. A brief global cognitive screening measure (the MoCA) will be administered at screen and at all subsequent study visits to ensure there is no cognitive decline during the study. The study psychometrist will be trained by Co-Investigator, [name]., MIRECC neuropsychologist, and she will conduct periodic checks for adherence to the standardized neuropsychological test battery administration protocol.

